**Panel 1 Study Design**

**Panel 2 Study Procedures and Assessments**

Visit	Screening a	Baseline b	Treatment Period														Primary Outcome or Withdrawal f	Safety Follow-Up d
			1	2	3	4	5	6	7	8	9	10	11	12	13	14		
Visit Number	1	2	3	4	5	6	7	8	9	10	11	12	13	14	15	16	17	18
End of Week	-	0	1	2	4	8	12	16	20	24	28	32	36	40	44	48	52	
Day	-14/-7	0	7	14	28	56	84	112	140	168	196	224	252	280	308	336	364	
Visit Window (days) c			±3	±3	±3	±6	±7	±7	±7	±7	±7	±7	±7	±7	±7	±7	±7	+3
Baseline Procedures and Assessments																		
Signed informed consent	√ a	√																
Diagnosis (DSM-5 TM )	√ a	√ f																
Demographics (age, sex, race)	√ a	√ f																
Relevant social, medical and psychiatric history	√ a	√ f																
Height	√ a	√ f																
Inclusion/exclusion criteria	√	√																
Effectiveness Assessments																		
PANSS	√	√ g	√	√	√	√	√	√	√	√	√	√	√	√	√	√	√	√
CGI-S	√	√ g	√	√	√	√	√	√	√	√	√	√	√	√	√	√	√	√
PSP	√	√ g			√					√								√
NSA-4		√ g			√					√								√
QLS		√ g			√					√								√
WoRQ		√ g			√					√								√
Tool		√ g			√					√								√
MSQ		√ g			√					√								√
HEA		√ h																√
Pharmacokinetic Assessments																		
Blood sampling for Lu AF35700 and metabolite assay		√ g			√					√								√
Translational Medicines Assessmentsi																		
Blood sampling for gene expression profiling (RNA) j		√ i																√ i
Blood sampling for metabolomics/proteomics (plasma) l		√ i																√ i
Blood sampling for pharmacogenetics (optional) k		√ i																

Visit	Screening a	Baseline b	Treatment Period														Primary Outcome or Withdrawal e	Safety Follow-up d		
			3	4	5	6	7	8	9	10	11	12	13	14	15	16				
Visit Number	1	2	3	4	5	6	7	8	9	10	11	12	13	14	15	16	17	18		
End of Week	-	0	1	2	4	8	12	16	20	24	28	32	36	40	44	48	52			
Day	-14/-7	0	7	14	28	56	84	112	140	168	196	224	252	280	308	336	364			
Visit Window (days) c			±3	±3	±3	±6	±7	±7	±7	±7	±7	±7	±7	±7	±7	±7	±7	+3		
Safety Assessments																				

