  - o. Prolactin results will remain blinded throughout the study.
  - p. For *16159A-patients*, additional ECGs will be done; 1 ECG recording before the daily dose is switched to weekly dosing (preferably on the day the decision of switching from daily to weekly dosing is taken) and 1 ECG recording the day after the first weekly dose is taken.
  - q. The first dose of IMP should be taken after the Baseline Visit is completed. All treatment assignment and subsequent IMP assignment is done via the IVRS/IWRS. The IVRS/IWRS will be assessed at the unscheduled visit only if the dose adjustment requires dispensing of IMP.
  - r. The dose of IMP can be increased for efficacy or decreased for tolerability at scheduled or unscheduled visits from Week 1 Visit.
  - s. For *16159A-patients* and *16323A-patients*, ongoing concomitant medication in study 16159A and 16323A, respectively, must be transferred by the investigators to the 16159B eCRF. All prescription, non-prescription medications, and herbal medications taken during study 16159B will be recorded as concomitant medications.
  - t. Urine drug screen tests can be repeated any time during the study at the discretion of the investigator.
  - u. S-βhCG pregnancy test should be performed at the Screening Visit (Only for *Other-patients*), Visit 5, Visit 10 and the Primary Outcome/Withdrawal Visit for women of childbearing potential. Urine pregnancy tests can be performed at any time during the study at the discretion of the investigator.

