At the end of the 1st week (Week 1 Visit), all patients included in this long-term safety study 16159B will be treated with one antipsychotic, Lu AF35700 at daily dose of 10 mg. At visits following the Week 1 Visit, according to the investigator's clinical judgement, the 10 mg/day dose can be increased to 20 mg/day based on the patient's response. Thereafter, the 20 mg/day dose can be reduced to 10 mg/day based on the patient's tolerability to treatment.

Patients previously participating in a study investigating Lu AF35700 will receive a down-titration wallet from the previous study. The down-titration will be done in a blinded fashion and will be completed at Day 7.

For patients who can potentially benefit from treatment with Lu AF35700 the discontinuation of the current oral antipsychotic medication will be gradually down-titrated according to the corresponding current SmPC or equivalent document/label and will be completed at Day 7.

**Only for patients who completed the 16159A study;** at the end of the 8th week (Week 8 Visit), according to the investigator's clinical judgment, the treatment with Lu AF35700 daily dosing regimen can be switched to a weekly 70 mg Lu AF35700 dosing regimen. The first weekly tablet will be taken 7 days after the last daily tablet. Thereafter, the switch from Lu AF35700 daily dosing regimen to Lu AF35700 weekly dosing regimen can be performed at any consecutive visit according to the investigator's clinical judgment. The first weekly tablet will be taken 7 days after the last daily tablet. The treatment with Lu AF35700 weekly dosing regimen can be switched back to daily dose of 10 mg for tolerability reasons or to daily dose of 20 mg for worsening of the patient's clinical status. This can occur at scheduled or unscheduled visits. The first daily tablet will be taken 7 days after the last weekly tablet.

The adjustment of Lu AF35700 dosing regimen (10 mg/day or 20 mg/day) will be left to the investigator's clinical judgement. The number of patients under weekly dosing regimen will be limited to 50 patients by the IVRS/IWRS.

All patients, including patients who withdraw, will be scheduled for a Safety Follow-Up Visit 42 days after last dose of IMP.

An internal Safety Committee at H. Lundbeck A/S has been established for Lu AF35700 and the committee will perform regular evaluations of the safety data.

No interim analysis is planned.

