**For patients who completed study 16159A (*16159A-patients*)**

The Baseline Visit will take place at the same visit as the Visit 12 (Primary Outcome Visit, end of Week 16) of the study 16159A.

After the baseline assessment, for eligible patients, the treatment with Lu AF35700 will be initiated at daily dose of 10 mg at Day 1 of study 16159B. In addition, for *16159A-patients*, the treatment (Lu AF35700, risperidone or olanzapine) received during study 16159A will be tapered down in a blinded fashion with wallets from study 16159A and will be completed in 7 days according to the following scheme:

- Patients randomised to Risperidone: 4 mg/day for the first 3 days; 2 mg/day for the 4 subsequent days, encapsulated tablets, orally, once daily
- Patients randomised to Olanzapine: 10 mg/day for the first 3 days; 5 mg/day for the 4 subsequent days, encapsulated tablets, orally, once daily
- Patients randomised to Lu AF35700: Placebo for 7 days, encapsulated tablets, orally, once daily.

At the end of the first week (Week 1 Visit), all patients will be treated with 10 mg/day Lu AF35700 only.

From the Week 1 Visit, according to the investigator's clinical judgment, the 10 mg/day dose can be increased to 20 mg/day based on the patient's response. Thereafter, the 20 mg/day dose can be reduced to 10 mg/day based on the patient's tolerability to treatment. This can occur at scheduled or unscheduled visits.

From the Week 8 Visit, the switch from Lu AF35700 daily dosing regimen to Lu AF35700 weekly dosing regimen can be performed at any consecutive visit according to the investigator's clinical judgment. The first weekly tablet will be taken 7 days after the last daily tablet. The Lu AF35700 weekly dosing regimen can be switched back to a daily dosing regimen of 10 mg/day for tolerability reasons or to 20 mg/day for worsening of the patient's clinical status. This can occur at scheduled or unscheduled visits. The first daily tablet will be taken 7 days after the last weekly tablet.

The number of patients under weekly dosing regimen will be limited to 50 patients by IVRS/IWRS.

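### The earliest increase to 20 mg/day is stated three ways, and a Week 1 Visit held early in its window can place it inside the antipsychotic taper

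*Protocol*

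**What the plan says.** The protocol gives three statements of when the dose may first go from 10 to 20 mg/day.

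- **From the Week 1 Visit onward.** Panel 2 footnote r, with no cohort limit: "The dose of IMP can be increased for efficacy or decreased for tolerability at scheduled or unscheduled visits from Week 1 Visit". The Panel 2 row for a possible dose change is ticked at Visit 3, which is the Week 1 Visit. The section 6.1 text for 16159A-patients opens "From the Week 1 Visit, according to the", and the synopsis agrees for that cohort. SAP Appendix IV repeats the tick and the footnote.
- **Only at visits after the Week 1 Visit.** Section 3.1, written for all patients: "At visits following the Week 1 Visit, according to the". The synopsis and section 6.1 texts for 16323A-patients and Other Patients use the same form of words.
- **By study day.** Panel 3 lists 10 mg/day for Days 1 to 3 and Days 4 to 7. It first lists 10 or 20 mg/day in the block that starts on Day 8.

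Panel 2 counts Baseline as Day 0 and puts the Week 1 Visit at Day 7 with a window of ±3 days. On the taper for patients from a lead-in study, section 3.1 says: "The down-titration will be done in a blinded fashion and will be completed at Day 7". The risperidone schedule in section 6.1 is "4 mg/day for the first 3 days; 2 mg/day for the 4 subsequent days"; olanzapine and quetiapine follow the same 3 + 4 day pattern. Patients who had Lu AF35700 in the lead-in study take placebo for those 7 days. Section 3.1 also says that at the Week 1 Visit all patients "will be treated with one antipsychotic, Lu AF35700 at daily dose of 10 mg".

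**The concern.** The text treats the Week 1 Visit as if it were the end of the taper, but the visit has a window and the taper does not. When the visit is early, one part of the protocol permits 20 mg/day, a second requires a later visit, and a third shows 10 mg/day on that date.

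Two sites that both follow the protocol could therefore give different doses on the same study day. One of them could combine 20 mg/day with a second antipsychotic that the design means to have finished. The wallet is blinded, so the investigator cannot tell an active taper from placebo. Section 14 allows no waivers, yet a monitor could not say consistently whether an increase on Days 4 to 7 is a deviation.

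**Working it through.** **Inputs.** Week 1 Visit: Day 7, window ±3 (Panel 2). Week 8 Visit: Day 56, window ±6 (Panel 2). Second taper step: Days 4 to 7, last taper day Day 7 (sections 3.1 and 6.1, Panel 3). First day on which Panel 3 lists 20 mg/day: Day 8.

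**Step 1, Panel 3's own figure.** Last taper day + 1 = 7 + 1 = Day 8. A Week 1 Visit on its nominal day with the new dose taken the next day also gives 7 + 1 = Day 8. At nominal timing, footnote r and Panel 3 agree.

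**Step 2, the window.** 7 − 3 = Day 4 and 7 + 3 = Day 10, so 7 visit days are permitted. Days 4, 5 and 6 (3 of 7) conflict with Panel 3 even if the new dose starts the day after the visit. Day 7 conflicts only if that day's tablet is taken after the visit, at the new dose. The synopsis allows morning or evening intake, so this is possible.

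**Step 3, possible days at 20 mg/day before the taper ends**, under footnote r:

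| Week 1 Visit on | New dose the same day | New dose the next day |
|---|---|---|
| Day 4 | 4 (Days 4–7) | 3 (Days 5–7) |
| Day 5 | 3 | 2 |
| Day 6 | 2 | 1 |
| Day 7 | 1 | 0 |

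The table takes the first dose as Day 1 on the Panel 2 count. Footnote q asks only that it follow the Baseline Visit. If the first dose is taken on Day 0, a Panel 2 Day 4 visit is treatment Day 4 − 0 + 1 = 5. Then 7 − 5 + 1 = 3 taper days remain, counting that day, and every entry above 0 falls by one. A Day 4 visit is inside the second taper step on either count.

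**Step 4, the rule of section 3.1.** After a Day 4 Week 1 Visit, the next visit can be an unscheduled one on 4 + 1 = Day 5. Footnote r allows dose changes at unscheduled visits, and section 3.1 does not confine increases to scheduled ones. This wording does not reliably exclude the overlap either.

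**Step 5, who is affected.** Per Panel 3, the active taper on Days 4 to 7 is risperidone 2 mg/day or olanzapine 5 mg/day for the comparator patients of study 16159A. SAP section 16 reports more than 500 patients, and SAP section 5 reports only 4 from study 16323A and no patients new to Lu AF35700. Nearly everyone is therefore in the cohort whose own text is the permissive one, but only its risperidone/olanzapine group has an active taper.

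**Step 6, the weekly switch, as a comparison.** 56 − 6 = Day 50 is the earliest Week 8 Visit. The last daily tablet is then on Day 49 or 50. The first weekly tablet comes 7 days later: 49 + 7 = Day 56 or 50 + 7 = Day 57.

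**The case against.** The best defence is that the protocol works at nominal timing: a visit on Day 7 and a new dose on Day 8 satisfy both footnote r and Panel 3. For 16159A-patients, the cohort that matters, footnote r and section 6.1 also agree with each other. Both points are true. They limit the conflict to early visits but do not remove it, because section 3.1 and Panel 3 apply to those patients as well. A plain difference between cohorts is not the explanation: section 3.1 contradicts the 16159A text, and footnote r contradicts the other two cohort texts.

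It can also be said that the share of permitted visit days is not a rate, and that the IVRS/IWRS may already block an early increase. The first point stands. On the second, section 6.4 describes no earliest-day check for 20 mg/day, but the system specification is not in the documents, so its absence is not established.

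A reader might infer three stronger things that the documents do not support.

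- **That the switch to 70 mg/week has the same fault**, because a Week 8 Visit may be held on Day 50 while Panel 3 starts that option on Day 56. The 7-day gap in sections 3.1 and 6.1 and Panel 3 puts the first weekly tablet on Day 56 or later.
- **That section 3.1 delays the increase to Day 11**, the lower limit of the Week 2 window (14 − 3). That requires unscheduled visits to be excluded, which section 3.1 does not do.
- **That the SAP's table of adverse events in the first 2 weeks (section 12.1.6) is blurred by early increases.** That table is split by previous treatment, not by dose, and Panel 3 itself permits both doses from Day 8. It mixes doses by design.

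**Conclusion.** The contradiction is real and lies in operative dosing instructions. Three statements of the earliest increase cannot all be followed when the Week 1 Visit falls on Days 4 to 6 (3 of 7 permitted days), or on Day 7 if that day's tablet is taken after the visit. For a Day 4 visit the possible overlap with an active previous antipsychotic is about 3 to 4 days in the risperidone/olanzapine group. It would be 2 days if the first dose was taken on Day 0 and the new dose started the day after the visit. The statement that everyone is on 10 mg/day Lu AF35700 alone at the Week 1 Visit also fails for these patients at any visit before the taper ends, even with no dose increase.

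The result rests on reading the Panel 2 window as applying to the Week 1 Visit without further restriction, and on a first dose on Day 1 unless stated otherwise. It says what the protocol permits. The documents do not show how many patients were raised early, and no view is taken on which rule is clinically right.

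**What to change.** The sponsor should reconcile the following to one statement of the earliest permitted increase: the synopsis texts for the three cohorts, the Visit 3 tick and footnote r in Panel 2 (with the copy in SAP Appendix IV), section 3.1, the three cohort texts in section 6.1, and Panel 3. The statement should be worded so that it still holds when the Week 1 Visit falls early in its window. The description of what patients are taking at that visit should be brought into line with it, and the IVRS/IWRS should be checked against the agreed wording. Which rule to adopt is the sponsor's clinical decision.

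The cost is a wording change in a handful of places and a check of the IVRS/IWRS settings. No analysis, sample size or endpoint changes.

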## List of Abbreviations and Definitions of Terms

AE	Adverse event
AIMS	Abnormal involuntary movement scale
ALT	alanine aminotransferase
AME	absorption metabolism and excretion
AP	alkaline phosphatase
APTS	all-patients-treated set
AST	aspartate aminotransferase
ATC	anatomical therapeutic chemical
AUC	area under curve
BARS	Barnes Akathisia Rating Scale
BUN	blood urea nitrogen
CAR	conditioned avoidance responding
CGI-S	Clinical Global Impression – Severity of Illness
CIOMS	Council for international Organizations of Medical Sciences
C max	maximum observed concentration
CNV	copy number variation
CPK	creatine phosphokinase
CRA	clinical research associate
CRF	case report form
CRO	Contract research organization
C-SSRS	Columbia-Suicide Severity Rating Scale
DSM-5™	Diagnostic and Statistical Manual of Mental Disorders, 5 th edition
ECG	Electrocardiogram
eCOA	electronic clinical outcome assessment
eCRF	electronic case report form
EMA	European Medicines Agency
EudraCT	European Union Drug Regulating Authorities Clinical Trials
FAS	full-analysis set
FDA	United States Food and Drug Administration
HBA1c	Glycated haemoglobin, Type A1c
hCG	human chorionic gonadotropin
HDL	high density lipoprotein
HEA	Health economic assessment
IB	Investigator's Brochure
ICF	Informed consent form
ICH	International Conference on Harmonisation of Technical Requirements for Registration of Pharmaceuticals for Human Use
ICMJE	International Committee of Medical Journal Editors

---

IEC	independent ethics committee
IMP	investigational medicinal product
IND	Investigational New Drug Application
INR	international normalised ratio of prothrombin time
IRB	institutional review board
ISM	international study manager
I-TMF	investigator trial master file
IVRS	interactive voice response system
LDH	lactate dehydrogenase
LDL	low density lipoprotein
LOCF	last observation carried forward
Lu	Lundbeck
MAD	Multiple ascending dose
MMRM	mixed model for repeated measurements
mSAS	Simpson Angus Scale
MSQ	Medication Satisfaction Questionnaire
NOAEL	no-observed-adverse-effect level
NSA-4	4-item Negative Symptom Assessment
PANSS	Positive and Negative Symptom Scale
PCS	potentially clinically significant
PD	pharmacodynamic(s)
PET	positron emission tomography
PK	pharmacokinetic(s)
popPK	Population pharmacokinetics
PR	specific ECG interval describing atrioventricular conduction
PRO	patient-reported outcome
PSP	Personal and Social Performance Scale
QLS	Quality of Life Scale
QP	qualified person
QRS	specific ECG interval describing ventricular depolarisation
QT	specific ECG interval describing ventricular depolarisation/repolarisation
QT c	heart-rate corrected QT interval
QT cF	heart-rate corrected QT interval using Fridericia's correction formula
RR	specific ECG interval describing the ventricular depolarisation/repolarisation cycle
SAE	serious adverse event
SD	standard deviation
SmPC	Summary of Product Characteristics
SNP	single-nucleotide polymorphism
SOC	system organ class
SOP	standard operating procedure
SUSAR	suspected unexpected serious adverse reaction

TEAE	treatment-emergent adverse event
$t_{\max}$	time to maximum observed concentration
TMF	trial master file
TooL	Tolerability and Quality of Life
TRS	Treatment-resistant schizophrenia
WoRQ	Readiness for Work Questionnaire

# 1 Introduction

## 1.1 Background

### 1.1.1 Overview

Schizophrenia is a severe, complex, chronic, and disabling psychiatric disorder with a lifetime prevalence of around 1%. Schizophrenia is characterised by profound disturbances in thinking, perception, and emotion and the clinical manifestation of the disease encompasses a wide range of symptoms such as positive symptoms (for example, delusions, hallucinations, and disorganised behaviour), negative symptoms (for example, affective flattening, social withdrawal, anhedonia, and poverty of speech), and symptoms of cognitive impairment (for example, impaired executive functioning, working memory, and attention deficits).

Numerous antipsychotics have been developed which all rely on the same underlying mechanism, namely interfering with dopamine receptors, and more specifically, dopamine D2 receptor antagonism. Therapies with phenothiazines, such as haloperidol and thiothixene, are effective but induce extra pyramidal symptoms (EPS) such as dystonia, muscle rigidity, tremor, and akathisia. Long-term effects, which develop after months to years of therapy, also include tardive dyskinesia. The above-mentioned drugs are referred to as typical or conventional antipsychotics and the adverse effects appear to be directly related to the dopamine D2 receptor blockade in the basal ganglia, whereas the antipsychotic effect of these compounds is dependent on reducing dopamine D2 mediated neurotransmission in the mesolimbic tracts (including the nucleus accumbens, stria terminalis, and the olfactory tubercle).

Lu AF35700 is a novel deuterated compound with affinity for dopaminergic, serotonergic, and  $\alpha$ -adrenergic receptors. The receptor binding profile and the pharmacological properties derived from animal experiments indicate that Lu AF35700 possesses antipsychotic activity combined with a benign tolerability profile.

The following sections 1.1.2 to 1.1.6 provide an overview of the nonclinical and clinical data currently available for Lu AF35700. Refer to the *Investigator's Brochure* for more detailed information.

### 1.1.2 Nonclinical Pharmacology Data

Lu AF35700 is a novel deuterated compound with affinity for serotonergic, dopaminergic, and  $\alpha$ -adrenergic receptors, and acts as an antagonist of those receptor types. The multi-receptor profile of Lu AF35700 is believed to have an antipsychotic effect.

Lu AF35700 has similar high affinity for the human serotonergic 5-HT2A and 5-HT6 receptors. Like “atypical antipsychotics”, the affinity for the human 5-HT2A receptor is substantially

higher than for the dopamine D2 receptor. Distinctively, Lu AF35700 has higher affinity for the human dopamine D1 receptor than it has for the human dopamine D2 receptor.

The *in vitro* receptor profile of high affinity for 5-HT2A and 5-HT6 receptors and low affinity for dopamine D2 receptors was confirmed by *in vivo* occupancy studies. The predicted steady-state concentration resulting in 50% target occupancy (EC50) was calculated based on *in vivo* occupancy and pharmacokinetic (PK) data from rats. The EC50 for 5-HT6 (12 ng/mL) and 5-HT2A (20 ng/mL) receptors is equipotent and much lower than for dopamine D1 (115 ng/mL) and dopamine D2 (255 ng/mL) receptors.

The potent binding to dopamine D1 receptors combined with a lower affinity for the dopamine D2 receptors is believed to result in a beneficial efficacy profile and a tolerability profile without the troublesome adverse effects associated with extensive dopamine D2 receptor blockade, such as extrapyramidal symptoms (EPS), hyperprolactinaemia, sexual dysfunction, and dysphoria/anhedonia. Furthermore, given the lack of muscarinic receptor blockade, it is expected that Lu AF35700 will not have a negative impact on cognitive performance related to muscarinic receptor inhibition.

In animal models, Lu AF35700 inhibited conditioned avoidance responding (CAR), amphetamine-induced hyperactivity, and phencyclidine (PCP)-induced hyperactivity at doses having no sedative or motor inhibiting effects, indicative of antipsychotic potential combined with few side effects.

[figure not shown]
Lu AF36152 is the major metabolite of Lu AF35700 and has a pharmacological *in vitro* and *in vivo* profile which is similar to that of Lu AF35700 although it is less potent *in vivo*.

